2.0 OBJECTIVES:

The primary objectives of this study are:

- 2.1 **Homogeneity of the metabolism of prostate cancer metastases:** To explore the FDG and CMET metabolism in tumors by PET in progressive prostate cancer, on a site by site basis.

2.1 **Diagnostic ability:** To explore the diagnostic ability of FDG and, in selected cases ¹¹C-methionine, by comparing PET scanning to standard of care diagnostic studies, which include the 99m-Tc bone scan, computed tomography, and magnetic resonance imaging.

2.2. **Treatment effects:** To explore changes in the relative tumor uptake, as defined by such quantitative measures as the standardized uptake value (SUV) and the total lesion metabolism (TLM), for FDG and ¹¹C-methionine after systemic therapy(ies). To determine which tracer, FDG or CMET, surrogates for glucose metabolism and amino acid synthesis respectively, is the superior predictor of treatment response.

2.3 FDHT Imaging: In selected patients who are progressing and have advanced androgen-independent prostate cancer, we will develop pilot data on the in vivo targeting and biokinetics of F-18 FDHT by PET imaging. When feasible, biopsy samples will be obtained from index lesions in order to correlate the level of FDHT uptake with androgen receptor expression, as determined by immunohistochemistry.

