One hypothesis under study in this trial is whether ¹¹C- methionine is more effective in visualizing androgen independent prostate cancer by PET imaging. The essential amino acid, ¹¹C- methionine is a tracer that has been used to image a variety of human tumors.(16-18) In a preliminary report from Nilsson and coworkers, 12 patients with androgen independent prostate cancer underwent PET imaging with ¹¹C- methionine. Uptake of the radiotracer was discovered in all known sites of bone and soft tissue lesions of patients visualized by standard bone scintigraphy or cross sectional imaging.(19) Ten patients had repeat PET scans. Those who responded to treatment had a reduced uptake of the radiotracer with no changes in the images generated by standard techniques. Our ongoing results show that 93% of index lesions were visible using ¹¹C-methionine and 83% visible using FDG.(1) These biodistribution and metabolic findings require additional verification in a larger series.

¹¹C-methionine and ¹⁸FDG whole body imaging

We have performed a preliminary comparative study of ¹¹C-methionine and ¹⁸F-FDG in 10 patients with prostate cancer, who were referred for PET imaging with progressive prostate cancer, as defined by serially rising PSA values and one or more new ("index") lesions on bone scan. Among the 10 patients, there were 13 such index lesions on bone scans. ¹¹C-methionine imaged 12/13 (93%), and ¹⁸F-FDG 11/13 (83%) index lesions. The one lesion not imaged by CMET was subsequently judged to be avascular necrosis, based on its pattern of resolution on subsequent bone scans. ¹¹C-methionine is very rapidly cleared from the blood, with rapid equilibration (10 minutes) in the tumor. The tumor uptake of ¹¹C-methionine is consistently high, with standard uptake values (SUVs) ranging from 4.9 to 11.6. We have therefore shown that high-quality whole body PET imaging is feasible with ¹¹C-methionine, despite the short 20-min physical half-life of carbon-11.

As accrual to the study has been limited by the need to generate ¹¹C-methionine immediately prior to administration, and based on our preliminary results showing that a higher percentage of tumors are visualized with FDG than previously anticipated, we plan to perform FDG scans in all patients, and ¹¹C-methionine when it is available. In cases where uptake is visible with FDG, repeat studies will be conducted after therapeutic intervention.

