12.0 BIOSTATISTICAL CONSIDERATIONS

To assess the diagnostic implications of PET scanning with ¹¹C-methionine and FDG, the sensitivity and specificity will be estimated by comparing PET scan results to "standard of care" diagnostic measures that include the 99m-Tc bone scan, computed tomography, and magnetic resonance imaging. Each patient will receive these standard diagnostic measures and PET scanning with both ¹¹C-methionine and FDG. The diagnostic

"standard of care" scan (bone scan, CT or MRI) will be recorded as positive or negative for each site: bone and bone marrow and/or soft tissue

The sensitivity of PET imaging with ^{11}C -methionine or FDG is defined as the ability of PET scanning to identify those metastatic lesions diagnosed by standard diagnosis using bone scan, CT, or MRI as "gold standard" and is determined by the proportion of patients with positive lesions as diagnosed by standard method who were identified by the PET imaging. The sensitivity will be measured for both androgen-dependent and androgen-independent prostate cancer patients, and on a site by site basis (bone and bone marrow, and soft tissue).

Assuming at least one site in each patient is assessed positive by the gold standard, the sensitivity of FDG and ^{11}C -methionine can be conservatively estimated to within ± 0.16 . The total sample size for this study is 265.

To explore changes in metabolism during treatment based on PET imaging, the average SUV value will be recorded at 4 weeks, 12 weeks, and 6 months following the baseline scan. Summary measures such as the slope of the SUV trajectory and the area under the SUV curve will be recorded separately for FDG and ^{11}C -methionine.

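### Section 12.0 states sensitivity to within ±0.16 beside a total of 265 patients, but 265 give about ±0.06 at 95%; ±0.16 fits about 38, and the ¹¹C-methionine denominator is not fixed

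*Combined protocol and SAP*

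**What the plan says.** Section 12.0 defines sensitivity at the patient level: it "is determined by the proportion of patients with positive lesions as diagnosed by standard method who were identified by the PET imaging". It gives every patient both tracers: "Each patient will receive these standard diagnostic measures and PET scanning with both" ¹¹C-methionine and FDG. It plans separate estimates: "The sensitivity will be measured for both androgen-dependent and androgen-independent prostate cancer patients, and on a site by site basis", the sites being bone and bone marrow, and soft tissue.

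The precision statement follows. It opens with a premise, "Assuming at least one site in each patient is assessed positive by the gold standard", and concludes that the sensitivity of FDG and ¹¹C-methionine "can be conservatively estimated to within" ±0.16. The next sentence reads: "The total sample size for this study is 265." The section does not say that 265 was derived from ±0.16. It gives no confidence level, no anticipated sensitivity, no n behind ±0.16 and no group sizes.

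Other sections differ on who receives ¹¹C-methionine. The diagnostic objective in Section 2.0 is "To explore the diagnostic ability of FDG and, in selected cases ¹¹C-methionine". Section 3.3 says "we plan to perform FDG scans in all patients, and ¹¹C-methionine when it is available". The summary in Section 1.0 allows FDG to be given alone.

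**The concern.** The two adjacent sentences are the plan's only precision figure and its only sample size, so a reader will take them together. They do not correspond: 265 patients estimate a proportion far more tightly than ±0.16.

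The reader therefore cannot tell which estimate ±0.16 describes. If it is FDG in the whole sample, the figure is much too wide and does not explain 265. If it is a smaller set, such as the ¹¹C-methionine patients or one androgen-status group, the set and its size are missing and the figure cannot be verified. Diagnostic ability is listed among the primary objectives, and a tracer or group with few reference-positive patients could be estimated less precisely than the plan states.

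**Working it through.** **Inputs from Section 12.0.** Half-width 0.16, for both tracers. Total 265. The unit is the patient, so clustering of lesions within patients does not enter. Every patient gets both tracers and is assumed to be reference-positive. Hence n = 265 for each tracer.

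**Assumptions, because the plan is silent.** Two-sided 95% confidence (z = 1.96) and a sensitivity of p = 0.5. The second is the widest case and the natural reading of a conservative estimate. Other values are shown below.

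**Step 1: attempt to reproduce ±0.16 from 265.** Half-width = z × √(p(1−p)/n).

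1.96 × √(0.25/265) = 0.060.

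The exact (Clopper-Pearson) half-width at 132 of 265 is 0.062. The stated figure is 0.16/0.0602 = 2.7 times the computed one.

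**Step 2: vary the confidence level, n = 265, p = 0.5.**

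| Confidence | Half-width |
|---|---|
| 90% | 0.051 |
| 95% | 0.060 |
| 99% | 0.079 |
| 99.9% | 0.101 |

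Any other p gives a narrower interval. To reach 0.16, z would have to be 0.16 × 2 × √265 = 5.2. Wilson, continuity-corrected and one-sided versions do not reach 0.16 either. Nor does a Bonferroni adjustment over eight estimates, which gives 0.084 with 265 patients and 0.119 with half of them.

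**Step 3: find the n that ±0.16 implies.** n = p(1−p) × (z/0.16)².

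At p = 0.5 and 95%: 0.25 × (1.96/0.16)² = 37.5, so 38 patients, about one-seventh of 265. At 90% it is 27 and at 99% it is 65.

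At 95%, by assumed sensitivity:

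| Sensitivity | n, normal approximation | n, exact |
|---|---|---|
| 0.5 | 38 | 41 |
| 0.7 | 32 | 36 |
| 0.8 | 25 | 29 |
| 0.9 | 14 | 19 |

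**Step 4: see what smaller denominators would give.** The documents state none, so these are illustrations only (p = 0.5, 95%).

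| Reference-positive patients | Half-width |
|---|---|
| 133 (half of 265) | 0.085 |
| 100 | 0.098 |
| 50 | 0.139 |
| 38 | 0.159 |
| 25 | 0.196 |

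**Step 5: look for the ¹¹C-methionine n.** Section 12.0 implies 265. Section 2.0 limits the tracer to selected cases, Section 3.3 makes it depend on availability, and Section 1.0 permits FDG alone. None gives a number, so n is undetermined for the protocol as a whole.

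**Step 6: test the all-positive premise.** Section 5.1 admits patients on a sustained PSA rise alone, and Section 1.0 includes localized disease and rising PSA. Some of these patients may have no positive site on bone scan, CT or MRI. The ±0.060 for FDG is therefore a best case, conditional on that premise.

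**The case against.** The strongest reply is that nothing stated is false. A claim of precision to within ±0.16, described as conservative, is a bound. If the true half-width is 0.06, the bound holds, and the plan never says 265 was calculated from it. That stands for FDG in the whole sample, where the discrepancy is in the safe direction. But a bound 2.7 times too wide neither describes nor justifies 265, and the argument does not carry over to ¹¹C-methionine, whose n is unknown.

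A second reply is that ±0.16 was meant for a smaller group. The sentence before it introduces androgen-status groups and sites, and a worst-case figure for the smallest group would explain both the wording and the width. This reading is possible and cannot be excluded. Equally, the text names no group and no size, and it attaches ±0.16 to both tracers alike. If this was the intention, the group and its n still have to be stated.

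A third reply is that the objectives are largely exploratory and that no test or decision rule uses ±0.16. That limits the consequence. It does not make the plan's only precision figure interpretable.

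It is also fair that the 95% level and p = 0.5 are not the document's own inputs. The mismatch does not depend on them, as Step 2 shows.

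**Conclusion.** The concern holds. On Section 12.0's premises, 265 patients give about ±0.06 for each tracer (two-sided 95%, p = 0.5, both assumed), and ±0.16 corresponds to about 38 patients. No conventional confidence level or assumed sensitivity pairs 0.16 with 265.

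The practical weight differs by estimate. For FDG over all patients, ±0.16 is an over-wide but safe bound. For ¹¹C-methionine and the androgen-status groups, it cannot be verified. In the worst case (p = 0.5, 95%), any of these with fewer than about 38 reference-positive patients would fall short of it; at higher sensitivities the threshold is lower. The documents do not show whether any group is that small, and they do not show why the two figures differ. This should be corrected, but it is not evidence that the study is too small.

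**What to change.** In Section 12.0, replace the precision sentence with one that carries its confidence level, assumed sensitivity and denominator. For example: *Assuming a sensitivity of 0.5 (the widest case), the two-sided 95% half-width for FDG is about 0.06 if all 265 patients are reference-positive.* Keep the all-positive premise only as that stated condition. Beside it, give the half-width for the number of reference-positive patients actually expected (for illustration, about ±0.085 if half are positive).

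Then:

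- Reconcile Section 12.0 with Sections 1.0, 2.0 and 3.3 on who receives ¹¹C-methionine, and give that tracer's expected n and its own half-width (for illustration, 100 patients give about ±0.10 and 38 about ±0.16).
- Give the expected n and half-width for the androgen-dependent and androgen-independent groups.
- If ±0.16 was meant for one of these groups, name the group and its size.
- State the basis for 265, or say that precision did not set it.
- Do not use the pilot rates in Sections 3.3 and 3.4 (12/13 and 11/13 index lesions; 71% concordance across 157 lesions in 18 patients) as patient-level sensitivities, because they count lesions.

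The cost is a few sentences in Section 12.0 and consistent wording on ¹¹C-methionine elsewhere. The sponsor will need to forecast tracer availability, the androgen-status split and the reference-positive rate, or show a range where it cannot. No extra patients or new data collection are needed.

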13.1 RESEARCH PARTICIPANT REGISTRATION AND RANDOMIZATION PROCEDURES

13.2 Research Participant Registration (PPR)

The following person(s) can obtain informed consent:

[name]
[name]
[name], PhD

Confirm in the electronic medical record that the patient has received the Notice of Privacy Practice. This must be obtained before the eligibility confirmation and obtaining of the research informed consent.

Confirm eligibility as defined in the section entitled Criteria for Patient/Subject Eligibility.

Obtain written informed consent, by following procedures defined in section entitled Informed Consent Procedures.

All participants must be registered through the Protocol Participant Registration (PPR) Office at Memorial Sloan-Kettering Cancer Center. PPR is available Monday through Friday from 8:30am - 5:30pm at [contact]. The PPR fax numbers are [contact] and [contact]. Registrations can be phoned in or faxed. The completed signature page of the informed consent form, the completed signature page of the Research Authorization and a completed Eligibility Checklist must be faxed to PPR.

During the registration process registering individuals will be required to answer specific eligibility questions and provide the following information:

Registering Individual	[Last, First Name]
Notice of Privacy Status	[Yes, No, N/A]
Research Authorization	[Date]
MSKCC IRB Protocol#	
Attending of Record (if applicable)	[Last, First Name]
Consenting Professional	[Last, First Name]
Informed Consent Date	
Participant's Full Name	[Last, First Name]
Participant MRN	

14.1 PROTECTION OF HUMAN SUBJECTS

14.2 Privacy

It is the responsibility of the Research Staff to ensure that Memorial Sloan-Kettering Cancer Center has on file a written acknowledgment of receipt by the subject of the Center's Notice of Privacy Practices. If the subject has not already done so, he/she must sign such an acknowledgment before participating in this study.

MSKCC's Privacy Office may allow the use and disclosure of protected health information pursuant to a completed and signed Research Authorization form. The use and disclosure of protected health information will be limited to the individuals described in the Research Authorization form. A Research Authorization form must be completed by the Principal Investigator and approved by the IRB and Privacy Board.

15.1 INFORMED CONSENT PROCEDURES

Patients will be required to sign a statement of informed consent (appendix F), which meets the requirements of the code of Federal Regulations (Federal Register Vol. 46, No. 17, Jan. 27, 1981, part 50) and the IRB of this center.

Documentation of informed consent: The informed consent will be signed by the patient and consenting physician in triplicate. A signed original consent form is given to the patient. The second original is placed in the patient's medical record and the third original is kept on file in the office of clinical research.

15.2 Research Authorization

Procedures for obtaining Research Authorization: Before any protocol-specific procedures are carried out, investigators and/or designated staff will fully explain the details of the protocol, study procedures, and the aspects of patient privacy concerning research specific information. In addition to signing the IRB Informed Consent, all patients must sign the Research Authorization component of the informed consent form. The Research Authorization requires a separate

signature from the patient. The original signed documents will become part of the patient's medical record, and each patient will receive a copy of the signed documents.

